1.2 Sample Size/Accrual Rate

We anticipate the enrollment of approximately 20 patients during the study period at an enrollment rate of approximately 10 subjects per year.

1.3 Stratification Factors

The MTD determination and dose escalation are uniform per stratum.

1.4 Analysis of Secondary Endpoints

Responses will be reported as a secondary endpoint. Every report should contain all patients included in the study. For the response calculation, the report should contain at least a section with all eligible patients. Another section of the report may detail the response rate for evaluable patients only. However, a response rate analysis based on a subset of patients must explain which patients were excluded and for which reasons. It is preferred that 95% confidence limits are given.

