1. OBJECTIVES

1.1 Primary Objectives

- 1.1.1** To conduct a phase I study to evaluate the safety and tolerability of this combination of chemotherapy agents.
- 1.1.2** To determine the response of children with recurrent or refractory central nervous system tumors with this combination of chemotherapy agents.

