1.1 Study Design/Endpoints

This is a single arm phase I dose escalation study, designed to determine the safety of lenalidomide and vorinostat when administered to children with relapsed or progressive central nervous system tumors. The starting dose and schedule are indicated in the treatment plan section. The study will follow a standard 3+3 patient cohort escalation design with escalation through five dose levels. Thus, a minimum of 6 patients and a maximum of 20 patients will be required to establish a recommended phase II dose. At Johns Hopkins All Children's Hospital, approximately 50-60 patients with brain and spinal cord tumors come for evaluation and treatments. Many of these patients relapse or have progressive disease. We anticipate the enrollment of approximately 20 patients during the study period at an enrollment rate of approximately 10 subjects per year. With this sample size, the 80% confidence interval if two, four, six, eight and ten patients show responses will be (1.8%-16.8%), (5.9%-24.9%), (10.9%-32.5%), (16.2%-39.7%) and (21.8%-46.6%) respectively.

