Statistical analysis will be conducted at the completion of the study after accrual goals have been met. We will describe the baseline demographic and clinical characteristics, adverse events and response in all patients. Continuous variables will be summarized using mean, standard deviations, median, maximum and minimum values. Discrete variables will be summarized using counts and percentages with the corresponding 95% confidence intervals where appropriate. Time to event variables will be analyzed using Kaplan Meier methods. Progression free survival (PFS) and overall survival rates and the corresponding confidence intervals at fixed time points will be derived from the Kaplan Meier estimate. PFS will be defined as the time between date of first dose of the study therapy and date of progression or death, whichever occurs first. Patients will be censored on the date of last tumor assessment if they remain alive and do not have tumor progression. Surviving patients who did not receive any on-treatment tumor assessment will be censored on the date of first dose of study medication. A window of 1 week prior to the PFS rate time points will be applied to account for different tumor assessments dates, since not all patients adhere to scheduled dates. Descriptive statistics will be used to summarize time to event endpoints, if Kaplan Meier methods fail to provide estimates. All statistical analysis will be performed using SAS software version v 9.3 (SAS Institute, Inc., Cary, NC)

All toxicities will be graded on all patients that receive any amount of study drug. Only patients who receive 12 week of therapy will be used for final analysis. The dose escalation schema, definition of DLT, and endpoints are in section 5.

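### The 80% confidence intervals for response in SAP 1.1 are those for 30 patients, not the planned 20, and understate the uncertainty; the rank of response also differs between the two documents

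*SAP*

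**What the plan says.** **Sample size.** SAP 1.1 says that "a minimum of 6 patients and a maximum of 20 patients will be required to establish a recommended phase II dose", and then "We anticipate the enrollment of approximately 20 patients during the study period". SAP 1.2 repeats the figure of about 20. No visible text mentions 30 patients.

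**Precision.** SAP 1.1 introduces its precision figures with the words "With this sample size, the 80% confidence interval if two, four, six, eight and ten patients show responses will be". It then lists five pairs of limits, one for each of those counts in turn; they are set out in full in the first table of the working.

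**Reporting level.** Later in SAP 1.1: "Discrete variables will be summarized using counts and percentages with the corresponding 95% confidence intervals where appropriate". SAP 1.4 adds, for response: "It is preferred that 95% confidence limits are given". SAP 1.5.2 also asks for 95% intervals, in a sentence that closes its paragraph on sub-analyses.

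**Status of response.** Protocol 1.1.2, under primary objectives, reads "To determine the response of children with recurrent or refractory central nervous system tumors with this combination of chemotherapy agents". SAP 1.4 reads "Responses will be reported as a secondary endpoint".

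**The concern.** Two of the printed intervals fail on sight. Ten responders among 20 is 50%, yet the interval stops at 46.6%. Eight among 20 is 40%, yet the interval stops at 39.7%. An exact two-sided interval for a proportion always contains the observed proportion, so these limits cannot belong to 20 patients.

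These intervals are the only statement in the visible text of how well the trial will estimate the response rate. Protocol 1.2.3 intends the efficacy data to support recommendations for larger studies. Intervals that are too narrow and centred too low misinform anyone using the SAP to judge what a given number of responses would mean.

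Separately, the documents give response two different ranks. That should be settled before results are seen.

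**Working it through.** **Inputs.** n = 20 (SAP 1.1 and 1.2); x = 2, 4, 6, 8, 10 responders; 80% level; printed limits from SAP 1.1. The SAP does not name the interval method.

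**Formula.** Exact (Clopper-Pearson) limits with alpha = 0.20:

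- lower = the alpha/2 quantile of Beta(x, n - x + 1)
- upper = the 1 - alpha/2 quantile of Beta(x + 1, n - x)

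**Step 1: reproduce the printed figures.**

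| Responders | Printed in SAP 1.1 | Exact 80%, n = 30 | Exact 80%, n = 20 |
|---|---|---|---|
| 2 | 1.8-16.8% | 1.8-16.8% | 2.7-24.5% |
| 4 | 5.9-24.9% | 5.9-24.9% | 9.0-36.1% |
| 6 | 10.9-32.5% | 10.9-32.5% | 16.6-46.7% |
| 8 | 16.2-39.7% | 16.2-39.7% | 24.9-56.7% |
| 10 | 21.8-46.6% | 21.8-46.6% | 33.8-66.2% |

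With n = 30 all ten limits agree to the printed decimal; the largest difference is 0.04 points. With n = 20 no limit agrees.

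**Step 2: could another method at n = 20 explain them?** For 10 responders at 80%, Wald gives 35.7-64.3%, Wilson 36.2-63.8%, Agresti-Coull 36.2-63.8% and Jeffreys 36.1-63.9%. None is near 21.8-46.6%. A search over n = 11 to 60, these five methods and levels of 80%, 90% and 95% finds only the exact 80% limits at n = 30. The next best candidate, exact 80% at n = 31, misses by up to 1.3 points.

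**Step 3: check by hand.** The midpoint of the last printed interval is (21.8 + 46.6)/2 = 34.2%. That is close to 10/30 = 33.3% and far from 10/20 = 50%.

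**Step 4: size of the error at the same 80% level.** Widths are in percentage points, taken from unrounded limits.

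| Responders | Printed width | Correct width, n = 20 | Ratio |
|---|---|---|---|
| 2 | 15.0 | 21.8 | 1.45 |
| 4 | 19.0 | 27.0 | 1.42 |
| 6 | 21.6 | 30.1 | 1.39 |
| 8 | 23.5 | 31.8 | 1.35 |
| 10 | 24.8 | 32.4 | 1.31 |

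The correct intervals are therefore 31% to 45% wider. They also sit higher: for 10 responders the lower limit moves from 21.8% to 33.8%.

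**Step 5: the reporting level, kept separate.** Exact 95% limits at n = 20 are 1.2-31.7%, 5.7-43.7%, 11.9-54.3%, 19.1-63.9% and 27.2-72.8%, with widths of 30.5, 37.9, 42.4, 44.8 and 45.6 points. For 4 responders the width goes from 19.0 (printed) to 27.0 (correct n, same level) to 37.9 (correct n, 95% level). Only the first of these two steps corrects an error.

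**The case against.** **A reader might infer that the 80%/95% difference is the fault, and that the SAP shows only about half the uncertainty the report will show.** The arithmetic is right: the 95% widths at n = 20 are 1.8 to 2.0 times the printed widths (45.6/24.8 = 1.84; 30.5/15.0 = 2.03). But this merges two effects. The SAP labels its planning intervals as 80%, so no reader is misled about the level. The 95% wording is soft: where appropriate in SAP 1.1, and a preference in SAP 1.4. In SAP 1.5.2 it is unclear whether the sentence governs the main response analysis or only the sub-analyses. Using one level for planning and another for reporting is permissible. The error is the 31% to 45%.

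**A reader might infer that the documents disagree on what the trial is chiefly judged on.** They do not. Protocol 1.1.1 puts safety and tolerability first, and SAP 1.1 describes a study designed to determine safety. Only the rank of response differs. The visible text gives no hypothesis test, alpha allocation or decision threshold for response, so relabelling it changes no visible calculation.

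**The intervals do not justify the sample size.** This stands. SAP 1.1 takes the range of 6 to 20 from the 3+3 design and about 20 from expected enrollment. The intervals follow as description, so correcting them does not by itself alter the stated basis for 20.

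**Perhaps 20 is the wrong number, not the intervals.** This cannot be excluded. Five dose levels with 6 patients each would give 5 x 6 = 30, but that is an inference; the SAP does not say where 30 came from. The fix has to allow for it.

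**Conclusion.** The point holds. As written, SAP 1.1 attaches exact 80% intervals for 30 patients to a planned and maximum size of 20. All five are wrong for that size, and two exclude the observed rate. At the SAP's own 80% level the correct intervals are about 31% to 45% wider and lie higher.

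The different status of response in Protocol 1.1.2 and SAP 1.4 is a real inconsistency, but a secondary one.

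The replacement figures rest on two assumptions: that 20 is the intended number, and that all 20 patients are in the response denominator, as the all-eligible rule in SAP 1.5.2 would have it if all 20 are eligible. SAP 1.1 also restricts the final analysis to patients with 12 weeks of therapy, and it allows as few as 6 patients. Either would give a smaller denominator, for which the n = 20 figures would not apply.

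**What to change.** 1. In SAP 1.1, replace the printed intervals. Name the exact (Clopper-Pearson) method and show both levels:

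| Responders of 20 | Exact 80% | Exact 95% |
|---|---|---|
| 2 (10%) | 2.7-24.5% | 1.2-31.7% |
| 4 (20%) | 9.0-36.1% | 5.7-43.7% |
| 6 (30%) | 16.6-46.7% | 11.9-54.3% |
| 8 (40%) | 24.9-56.7% | 19.1-63.9% |
| 10 (50%) | 33.8-66.2% | 27.2-72.8% |

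2. State that these figures assume all 20 patients are in the response denominator, under the all-eligible rule of SAP 1.5.2, and reconcile that rule with the 12-week restriction in SAP 1.1.
3. If the intended size was not 20, reconcile the stated size and the intervals instead, throughout SAP 1.1 and 1.2.
4. Give response the same status in Protocol 1.1.2 and SAP 1.4. If it stays primary, move it out of the section on secondary endpoints.

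The cost is replaced figures and a few lines of wording, with a less favourable stated precision. If 20 stands as the planned number, no patients are added.

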1.5 Reporting and Exclusions

1.5.1 Evaluation of Toxicity

All patients will be evaluable for toxicity from the time of their first treatment.

1.5.2 Evaluation of Response

All patients included in the study must be assessed for response to treatment, even if there are major protocol treatment deviations or if they are ineligible. Each patient will be assigned one of the following categories: 1) complete response, 2) partial response, 3) stable disease, 4) progressive disease, 5) early death from malignant disease, 6) early death from toxicity, 7) early death because of other cause, or 9) unknown (not assessable, insufficient data). [Note: By arbitrary convention, category 9 usually designates the “unknown” status of any type of data in a clinical database.]

All of the patients who met the eligibility criteria (with the possible exception of those who received no study medication) should be included in the main analysis of the response rate. Patients in response categories 4-9 should be considered to have a treatment failure (disease progression). Thus, an incorrect treatment schedule or drug administration does not result in exclusion from the analysis of the response rate. Precise definitions for categories 4-9 will be protocol specific.

All conclusions should be based on all eligible patients. Subanalyses may then be performed on the basis of a subset of patients, excluding those for whom major protocol deviations have been identified (e.g., early death due to other reasons, early discontinuation of treatment, major protocol violations, etc.). However, these sub analyses may not serve as the basis for drawing conclusions

concerning treatment efficacy, and the reasons for excluding patients from the analysis should be clearly reported. The 95% confidence intervals should also be provided.
